5.5.8.1. Analysis

Correlations between change in NPI-C A+A score and change in SDI average total score and between change in NPI-C A+A score and change in SDI summed product score over time will be explored; Pearson and Spearman correlation coefficients will be calculated. Scatter plot of change in scores of the 2 assessment scales over time will be presented for each intervention group.

A mediation analysis will be performed to examine the mediating role of improvement in sleep assessed by change from baseline in SDI score on change from baseline in NPI-C A+A score provided that both endpoints demonstrate a statistically significant difference between seltorexant and placebo. This analysis will assess the extent to which change in NPI-C A+A score may be mediated by or independent of change in SDI score based on observed data (i.e., data collected at each time point without carrying forward previous values) at Day 43. The analysis will consider both change in NPI-C A+A score and change in SDI score as continuous variables.

• Simulation-based Counterfactual Approach: this analysis introduced by Imai et. al obtains the natural direct effect and natural indirect effect using numerical simulations. The approach uses parametric bootstrapping to construct the point estimate and its uncertainty estimates for direct effect and indirect effect from the bootstrap sampling distribution. For each bootstrapped sample, change from baseline in NPI-C A+A score and change from baseline in SDI score will be analyzed. The ANCOVA analysis of change in NPI-C A+A score from baseline will include factors for treatment (placebo and seltorexant dose groups), change from baseline (Day 1, predose) in SDI score, treatment-by-change from baseline in SDI score

Statistical Analysis Plan 42847922ALZ2001

interaction if the interaction is significant, and baseline NPI-C A+A score as a covariate. The ANCOVA analysis of change in SDI score will include factors for treatment (placebo and seltorexant dose groups), and baseline NPI-C A+A score as a covariate. Estimate of the controlled direct effect will be obtained by plugging in the estimated coefficient values and the mean level of change in SDI score into the analytic expressions.

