Excessive daytime sleepiness, sundowning, and insomnia are among the most common sleep disturbances in dementia due to AD, and originate from changes in sleep architecture and the circadian rhythm (Wang & Holtzman, 2020). Neuronal and synaptic damage that occur as a result of AD pathology in circadian regulating areas of the brain (e.g. hypothalamic suprachiasmatic nucleus) increase the dysfunction of cellular circadian rhythms. This damage is believed to be an underlying cause of the sleep disturbances seen in AD, including increase in fragmented daytime naps, reduced rapid eye movement (REM) and non-rapid eye movement (NREM) slow wave sleep

(SWS) duration and decreased sleep efficiency, coupled with increased wakefulness after sleep onset (WASO) (Liguori 2016).

Changed sleep architecture and circadian rhythm dysregulation in AD patients is correlated with other behavioral manifestations of BPSD, such as depressive mood, apathy, and aggressiveness (Moran 2005; Shin 2014; Mulin 2011). It has also been suggested that symptoms such as aggressiveness are consequences of the same underlying problem, e.g., disturbance of rest/activity and sleep-wake rhythms due to circadian rhythm disturbance (Moran 2005). Recent preclinical evidence also supports an additional important role of orexin in modulating behavior such as aggression through the activation of a small population of glutamic acid decarboxylase 2-expressing neurons in the lateral habenula via OX2R, which is consistent with other evidence of the role for orexin in other motivated behaviors (Flanigan 2020). In this study, in addition to demonstrating that cell-type-specific knockdown of OX2R reduces aggression and preference for aggression-paired contexts without affecting locomotor behavior, it was also seen that systemic administration of an OX2R antagonist reduces aggression and preference for aggression-paired contexts without affecting motor behavior in the open field test in mice. Thus, seltorexant as an orexin 2 antagonist has the potential to have a direct anti-aggression activity in AD patients with aggression.

Seltorexant has shown consistent results in improving total sleep time, reducing wake after sleep onset, and improving sleep efficiency in both adults and elderly patients with insomnia disorder as well as patients with MDD. Further, seltorexant 20 mg has shown the ability to reduce sleep fragmentation in patients with MDD leading to improved sleep quality and more restful sleep.

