•	Depressive symptoms as assessed by the Geriatric Depression Scale, Informant version (GDSI).	•	Change from baseline on GDSI Total score at Day 43.			
•	The association between treatment effect of seltorexant in sleep and treatment effect in agitation/aggression	•	Correlation between change in NPI-C A+A and change in SDI total score, and mediation effect on change in NPI-C A+A through change in SDI total score			
•	Cognitive symptoms	•	Change from baseline to Day 43 on Alzheimer's Disease Assessment Scale Cognitive subscale 14-item version (ADAS-Cog-14) composite cognitive score and from screening to Day 43 on the Mini- Mental State Examination (MMSE) total score.			
Safety						
To investigate the effect of seltorexant versus placebo on the following in participants with probable AD with clinically significant agitation/aggression:						
•	Safety and tolerability of seltorexant	•	Change from baseline in Vital signs, Clinical Labs (chemistry, hematology, urinalysis), ECG, C-SSRS, and Treatment Emergent Adverse Events (TEAEs) including AEs of special interest (AESI).			

Refer to Section 8, Study Assessments and Procedures for evaluations related to endpoints.

HYPOTHESIS

The hypothesis for this study is that seltorexant 20 mg is superior to placebo in reducing aggression and agitation as measured by change in NPI-C A+A scores from baseline to Day 43 in participants with probable AD and clinically significant agitation/aggression.

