2. STATISTICAL HYPOTHESES

This study is designed to show that the treatment effect in improving agitation and aggression (as measured by change from baseline on Day 43 in NPI-C A+A score) of seltorexant 20 mg is superior to placebo in participants with probable AD with clinically significant agitation/aggression.

If μ_T is the mean change in NPI-C A+A total score for seltorexant group and μ_P is the mean change in NPI-C A+A total score for the placebo group, then the hypothesis can be written as follows:

 $\begin{array}{l} H_0: \, \mu_T \! - \! \mu_P \! \geq \! 0 \, \mathrm{vs.} \\ H_1: \, \mu_T \! - \! \mu_P \! < \! 0 \end{array}$

Superiority can be concluded if the two-sided p-value for the testing of the hypothesis above is less than 0.20.

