3. SAMPLE SIZE DETERMINATION

Assuming a treatment difference of 5 points in change from baseline in NPI-C A+A score between seltorexant 20 mg and placebo, a standard deviation of 10 (effect size of 0.5), and a 15% drop-out rate during the 6-week double-blind phase, 86 participants (randomized in 1:1 ratio to placebo and seltorexant 20 mg) will need to be enrolled in the double-blind phase, in order to achieve 80% power to detect treatment difference, at one-sided 0.1 significance level.

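### The mediation analysis requires a significant SDI difference as well as a significant NPI-C A+A difference, so no direct or indirect effect is estimated when only A+A is significant

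*SAP*

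**What the plan says.** The protocol (section 3, Other Exploratory) sets an objective on the association between the treatment effect in sleep and the treatment effect in agitation/aggression. One of its endpoints is the "mediation effect on change in NPI-C A+A through change in SDI total score". The synopsis and the SAP endpoint table (section 1.1) carry the same endpoint. None of the three attaches a significance condition.

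SAP section 5.5.8.1 gives the method, a simulation-based counterfactual approach yielding natural direct and natural indirect effects and a controlled direct effect. Its stated purpose is to assess "the extent to which change in NPI-C A+A score may be mediated by or independent of change in SDI score". The same paragraph makes the analysis conditional: it is performed "provided that both endpoints demonstrate a statistically significant difference between seltorexant and placebo". No alternative is given for the case where only A+A is significant, and no reason is given for the condition.

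Two details of the condition are left open. The 0.20 threshold in SAP section 2 ("Superiority can be concluded if the two-sided p-value for the testing of the hypothesis above is less than 0.20") belongs to the primary hypothesis, and no level is stated for SDI. SAP section 5.4.1.2 defines and analyses two SDI scores, the average total and the summed product, whereas the mediation paragraph refers only to the SDI score.

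**The concern.** The analysis is meant to say how much of any agitation benefit runs through sleep and how much does not. The protocol rationale (section 2.1) raises both routes: aggression as a consequence of disturbed sleep-wake rhythms, and the possibility that seltorexant "has the potential to have a direct anti-aggression activity in AD patients with aggression". A largely direct route would tend to show as a significant A+A difference with little movement on SDI. For that result pattern the SAP produces no estimate of either part.

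What is lost is a quantified answer. In a trial of this size a non-significant SDI result is compatible with no sleep effect and also with a moderate one. An indirect effect with its interval would show how much mediation the data can exclude; a p-value above the threshold does not.

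**Working it through.** **Inputs from the documents (SAP section 3; protocol section 9.2).** Difference 5 points, SD 10, one-sided alpha 0.10, power 80%, drop-out 15%, 86 randomised 1:1.

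**Inputs assumed.** The documents give no SDI effect size, no SDI power and no correlation between the A+A and SDI test statistics. These are varied below.

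**1. Reproduce the plan's figure.** Normal approximation, per arm:
n = 2 × [(z0.90 + z0.80) × SD/difference]² = 2 × [(1.2816 + 0.8416) × 10/5]² = 36.06, rounded up to 37, or 74 evaluable in total.
- Multiplying by 1.15: 37 × 1.15 = 42.6, rounded up to 43 per arm, 86 in total, the stated figure.
- Dividing by 0.85: 74/0.85 = 87.1, rounded up to 88.

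The stated 86 reproduces closely enough for the present purpose.

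**2. Evaluable participants and A+A power.** 86 × 0.85 = 73.1, or 36.55 per arm. The expected A+A test statistic is 0.5 × √(36.55/2) = 2.137. Power = Φ(2.137 − 1.2816) = 0.804, against 80% stated.

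**3. How often the analysis is skipped if SDI truly does not move.** Take the planned A+A effect, no SDI effect, and SDI significance at two-sided p<0.20. With uncorrelated statistics SDI passes by chance in 20% of trials, so both pass in 0.804 × 0.20 = 0.161 of trials and the skip rate among A+A-positive trials is 1 − 0.20 = 80%. With correlation, from the bivariate normal:

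| Correlation | Both pass | Skipped, given A+A significant | Skipped if SDI must favour seltorexant |
|---|---|---|---|
| 0 | 16.1% | 80% | 90% |
| 0.3 | 15.6% | 81% | 88% |
| 0.5 | 14.7% | 82% | 88% |

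**4. If SDI does have an effect.** Same threshold, correlation 0 to 0.5:

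| Assumed SDI effect | Skipped, given A+A significant |
|---|---|
| 0.2 SD | 60-65% |
| 0.3 SD | 43-49% |
| 0.5 SD | 14-20% |

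Expressed through SDI power instead, with A+A power 80%:
- SDI power 30%, correlation 0: both pass in 0.80 × 0.30 = 24%; skipped in 1 − 0.24/0.80 = 70%.
- SDI power 80%, correlation 0.7: both pass in 71%; skipped in 1 − 0.713/0.80 = 11%.

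**5. What a non-significant SDI result means.** At 36.55 per arm, a true SDI effect of 0.3 SD passes one-sided 0.10 in favour of seltorexant only about 50% of the time (Φ(0.3 × √(36.55/2) − 1.2816) = Φ(0.001)). So failing the SDI condition does not separate no sleep effect from a moderate one.

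**The case against.** The best defence is that the condition fits the objective. The objective speaks of an effect in sleep and an effect in agitation, which presupposes both, and the endpoint is mediation through SDI, not the direct effect. Protocol section 9.4.2 leaves exploratory analyses that it does not describe to the SAP, so a prespecified condition is a permissible choice. This stands against calling the SAP a breach of the protocol. It does not explain why the paragraph also sets out to measure the part independent of SDI and then withholds it when SDI is not significant.

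The defence can also point to much evidence on the same question that is reported whatever the p-values:
- the A+A and SDI contrasts with 80% CIs (SAP 5.3.2.1.1, 5.4.1.2.2);
- correlations and scatter plots for both SDI scores (5.5.8.1);
- actigraphy models and their correlation with the primary endpoint (5.7.2.1);
- the A+A effect by baseline NPI-12 sleep category (5.5.10, 5.7.4).

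If SDI truly does not move, the total A+A effect approximates the direct effect. A reader might therefore infer that a direct effect cannot be seen at all in the skipped case; the documents do not support that. What is missing is the formal split with its uncertainty, and the approximation relies on a near-zero SDI effect, which non-significance does not establish.

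Three further inferences also go too far:
- **That the condition tilts the reported evidence towards mediation.** When both endpoints pass, direct and indirect effects are both reported, and the indirect share also depends on how SDI relates to A+A. No such bias has been calculated. Selecting on A+A significance raises the expected A+A difference from 5.0 to about 5.8 points, but that conditions on A+A alone and says nothing about the SDI condition.
- **That direct activity is the study's alternative hypothesis.** It is a remark in the rationale; the stated hypothesis is superiority on A+A.
- **That mediation is worth running after any result.** With no A+A effect there is little to mediate, so a condition on A+A is defensible.

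**Conclusion.** The point holds as a low-cost improvement to an exploratory analysis. As written, the SAP produces no direct or indirect estimate when A+A is significant and SDI is not, although the endpoint is listed unconditionally and a non-significant SDI result in about 73 participants cannot stand in for the missing estimate.

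The share of A+A-positive trials affected is 80-82% if SDI has no true effect, and 11-70% across the assumed SDI powers and correlations. These ranges rest on a 0.20 two-sided threshold for SDI (or its one-sided 0.10 equivalent), which the SAP does not state, and on SDI effects and correlations that the documents do not give. The primary conclusion is untouched, and a direct effect is still estimated when both endpoints pass. SAP section 5.3.2.1.1 makes no multiplicity adjustment for efficacy endpoints, so there is no error-control reason to keep the SDI condition.

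**What to change.** In SAP section 5.5.8.1, remove the requirement that SDI be significant, so that the mediation analysis runs at least whenever NPI-C A+A is significant. State which SDI score is the mediator, average total or summed product, or run it for both. Report the direct and indirect effects with 80% CIs and label the analysis exploratory. If any significance condition is kept, state its level and sidedness and, if it involves SDI, the score it applies to.

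The method is already specified, so the cost is a short text change and possibly a second run for the second SDI score. The downside is that the intervals may be wide and inconclusive, particularly when the SDI effect is small.

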7. DISCONTINUATION OF STUDY INTERVENTION AND PARTICIPANT DISCONTINUATION/WITHDRAWAL

7.1. Discontinuation of Study Intervention

A participant's study intervention must be discontinued if:

- The participant (or legal representative) withdraws consent to receive study intervention
- The investigator believes that for safety reasons or tolerability reasons (eg, AE) it is in the best interest of the participant to discontinue study intervention
- Based upon the clinical judgment of the investigator, a participant may be withdrawn for lack of efficacy (ie, clinically significant worsening of agitation/aggression or other BPSD symptoms).
- Noncompliance with study drug administration defined as missing either 4 or more consecutive doses of study drug or a total of 8 or more doses during any 4-week period
- The participant persistently uses a disallowed medication as discussed with the sponsor's medical monitor or designee.
- The participant shows signals of acute suicidal ideation with a clear plan or intent at any time during the study; the participant should be referred to appropriate medical/psychiatric care.
- AST and/or ALT exceeds 5X ULN (confirmed by repeat testing).
- AST and/or ALT exceeds 3X ULN and total bilirubin exceeds 1.5X ULN (confirmed by repeat testing).
- Study drug blind is broken during the DB treatment phase

Follow-up assessments should be obtained according to the SoA. All participants who discontinue study drug in the DB treatment phase, will have an Early Withdrawal visit (Visit 6 in the SoA) and a Follow-up visit (Visit 7 in the SoA). Participants who discontinue study drug prior to Day 35 are encouraged to continue after the Follow-up visit (Visit 7 in the SoA) with additional follow-up visits every 2 weeks per the SoA until Day 57. If a participant discontinues study medication and enters the follow-up phase, other concomitant medications, including disallowed medication, may be started (see Section 6.8.1). Study intervention assigned to the participant who discontinued study intervention may not be assigned to another participant. Additional participants will not be entered to replace participants who discontinue the study early.

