Summary Measure: Difference in intervention means

Intercurrent Events	Name of Strategy for Addressing Intercurrent Events and Its Description
1. Treatment discontinuation of study drug without switching	Hypothetical strategy: as if the intercurrent event had not occurred
2. Switch of treatment	Hypothetical strategy: see above
3. Allowed rescue medication	Treatment policy strategy: all observed values of
(including use after treatment	the endpoint are used regardless of whether or not
discontinuation, but prior to DB	the participant had experienced this intercurrent
disposition)	event

Intercurrent events and their corresponding strategies:

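### The sleep-to-agitation mediation uses only observed Day 43 scores, so dropout driven by earlier worsening would bias it and its total need not match the primary difference

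*SAP*

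**What the plan says.** Protocol section 3 lists, among the other exploratory endpoints, the "mediation effect on change in NPI-C A+A through change in SDI total score". SAP 5.5.8.1 runs this analysis "provided that both endpoints demonstrate a statistically significant difference between seltorexant and placebo" and does so "based on observed data (i.e., data collected at each time point without carrying forward previous values) at Day 43".

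Two models are specified. The outcome model regresses change in NPI-C A+A on treatment, change in SDI (plus their interaction if significant) and baseline NPI-C A+A. For the mediator model, in which baseline NPI-C A+A is the only covariate, the SAP's wording begins: "The ANCOVA analysis of change in SDI score will include factors for treatment (placebo and seltorexant dose groups), and baseline NPI-C A+A score as a". Neither model uses an earlier post-baseline visit, and no imputation is named. SAP 5.5 names the full analysis set for exploratory analyses, but these models can use only participants who have both Day 43 scores.

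In SAP Table 1, the double-blind Day 43 window for NPI-C and SDI runs from Day 37 to the end of that phase. Follow-up visits of participants who stop before Day 35 carry separate EW labels.

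For Estimand 1, SAP 5.3.2 handles treatment discontinuation by a "Hypothetical strategy: as if the intercurrent event had not occurred". The estimator (SAP 5.3.2.1.1) is an MMRM with time as a factor. SDI is tested with the same type of model (SAP 5.4.1.2.2). Protocol 7.1 says "a participant may be withdrawn for lack of efficacy (ie, clinically significant worsening of agitation/aggression or other BPSD symptoms".

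**The concern.** The two endpoints are tested with models that use Days 15, 29 and 43. The mediation then splits an effect estimated from fewer people at one visit. A participant who worsens by Day 29 and leaves contributes to the MMRM through the earlier scores but is absent from the mediation.

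A likelihood-based repeated-measures model remains valid when dropout depends on scores already observed (MAR). A Day 43 ANCOVA that omits those scores does not. Protocol 7.1 makes dropout linked to worsening foreseeable.

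At stake is the reading of the mechanism. A report could show an MMRM difference beside direct and indirect effects that do not sum to it, with no explanation planned. Those effects could be too small.

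**Working it through.** **1. The plan's own figure.** SAP section 3 assumes a difference of 5, SD 10, one-sided alpha 0.1, 80% power and "a 15% drop-out rate during the 6-week double-blind phase".

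- n per arm = 2 × [10 × (1.2816 + 0.8416) / 5]² = 36.06
- 36.06 / 0.85 = 42.4, rounded up to 43 per arm, or 86 in total. This reproduces the stated size.

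**2. Who is left.** 86 × 0.15 = 12.9 and 86 × 0.85 = 73.1. Dropout could remove up to about 13 participants, leaving about 73. Anyone assessed at withdrawal from Day 37 onward stays in.

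**3. What the mediation splits.** Without the interaction, let the mediator model be M = a0 + a1·T + a2·B and the outcome model Y = b0 + b1·T + b2·M + b3·B. Here T is treatment, M change in SDI, Y change in NPI-C A+A and B baseline NPI-C A+A. The indirect effect is a1·b2, the direct effect b1, and the total b1 + a1·b2. By least-squares algebra, that total equals the treatment coefficient from regressing Y on T and B in the same participants. It is therefore the observed Day 43 contrast, which the MMRM estimate need not equal.

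**4. Size, first simulation** (400,000 per scenario). Only the difference, SD and dropout come from the documents. Assumed inputs: 50%, 80% and 100% of the effect present at Days 15, 29 and 43; adjacent-visit correlation 0.5, 0.7 or 0.8; true indirect effect 2 and direct effect 3; dropout logistic in the Day 29 change. Effects are in points of benefit. Shortfall = (5 − total) / 5.

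| Dropout slope per SD (odds ratio) | Total at correlation 0.5 / 0.7 / 0.8 | Shortfall |
|---|---|---|
| Both arms, 0.5 (1.6) | 4.92 / 4.96 / 4.91 | 1.6% / 0.8% / 1.8% |
| Both arms, 1 (2.7) | 4.83 / 4.73 / 4.68 | 3.4% / 5.4% / 6.4% |
| Both arms, 2 (7.4) | 4.61 / 4.41 / 4.34 | 7.8% / 11.8% / 13.2% |
| Placebo only, 1 (2.7) | 4.23 / 3.94 / 3.84 | 15.4% / 21.2% / 23.2% |

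In the placebo-only row the indirect effect is 1.82 / 1.78 / 1.76 and the direct effect 2.42 / 2.16 / 2.08. The mediated share is 1.82/4.23 = 43%, 1.78/3.94 = 45% and 1.76/3.84 = 46%, against a true 2/5 = 40%. Arm-wise MAR imputation from the earlier visits returned totals of 4.96 to 5.04 throughout.

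**5. Mediated share with equal slopes.** A re-run of this set-up, with its own assumed SDI scaling, gave 39% to 41% at slopes 0.5, 1 and 2.

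**6. Second simulation** (1,000,000 per scenario; true total 5, true indirect 1.5, so share 30%; correlation 0.5 and 0.7; realised dropout about 13-14%).

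- Dropout unrelated to outcome: totals 4.98 and 5.00.
- Worsening-driven in both arms: totals 4.70 and 4.63; shares 1.41/4.70 = 30% and 1.37/4.63 = 30%.
- Placebo only, with nobody leaving on seltorexant: totals 3.33 and 2.83, shortfalls of 33% and 43%; shares 1.29/3.33 = 39% and 1.27/2.83 = 45%.

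The MAR likelihood estimate was 4.97 to 5.01 in all of these. Direct plus indirect summed to the observed Day 43 total, apart from rounding.

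**7. At trial size** (43 per arm, assumed correlation 0.7, 15% dropout). Observed-case totals were 4.8 and 4.5 with worsening-driven dropout in both arms and 4.0 with placebo-only dependence. Joint MAR imputation by arm gave about 5.1, with essentially no penalty in root mean squared error.

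**The case against.** **Precision.** This is the strongest counter-argument. With 73.1 / 2 = 36.55 per arm, the standard error of the total is about 10 × √(2 / 36.55) = 2.3. Simulation put the sampling SD of the direct and indirect effects at about 2.2 and 1.1. The 10th to 90th percentile range of the mediated share was about 14% to 88% with no dropout bias. A bias of 0.2 to 0.3 points (both arms, slope 1) is about a tenth of a standard error. This stands and limits the importance of the point. It is not a reason to keep a data rule that discards information already collected.

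**Stakes.** The analysis is exploratory, is gated on both endpoints and feeds no stated decision. The SAP gives its data basis openly and does not promise to decompose Estimand 1. All of this stands.

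**Stronger readings the documents do not support.**

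- A reader might infer that only completers are analysed, or that everyone withdrawn for worsening is lost. The window opens at Day 37 and the Early Withdrawal visit includes NPI-C and SDI, so later withdrawals assessed in the window are included.
- A reader might infer that the effects cannot add up to the primary difference. If missingness depends only on arm and baseline NPI-C A+A, the totals agree in expectation.
- A reader might infer that the direct/indirect split, and so the mechanistic conclusion, will be wrong. With similar dropout mechanisms in both arms the share hardly moves. A material shift needs worsening to drive dropout on placebo alone. Protocol 7.1 gives one withdrawal rule for a blinded trial, so nothing in the documents points to that asymmetry.

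**Does the MMRM share the problem?** The SAP also describes the MMRM as observed-case. That does not remove the difference, because the MMRM uses the earlier visits.

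**Could follow-up visits fill the gap?** The SAP does not say whether values labelled Day 43 EW count as observed Day 43 data. By label they do not. If they did, off-drug data that Estimand 1 leaves out would enter.

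**Conclusion.** The point holds as a mismatch between the mediation and the models that gate it, with a possible bias of modest size. If dropout depends on earlier post-baseline scores, the total, direct and indirect effects are biased.

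Under the assumed inputs the total is 1% to 2% too small with weak dependence in both arms and about 3% to 13% too small with moderate to strong dependence; the mediated share barely changes. With placebo-only dependence the shortfall is about 15% to 23% and the share moves from 40% to 43-46%. The harsher variant with no seltorexant dropout gives 33% to 43%. Unrelated dropout gives no bias.

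The trajectory, correlations, mediated fraction and dropout slopes are assumptions, so the documents cannot settle the actual size or direction. The primary test is untouched. This is a cheap improvement to an exploratory analysis.

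**What to change.** In SAP 5.5.8.1, replace the restriction to observed Day 43 data as follows.

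- Impute missing Day 43 NPI-C A+A and SDI jointly, separately by arm, under MAR from baseline, Day 15 and Day 29 values of both scales. Apply the Estimand 1 data cut-off, which is the double-blind disposition day.
- Fit the two stated models in each imputed dataset and pool the direct, indirect and total effects.
- Keep the observed-case version as a sensitivity analysis.
- Report the total effect beside the Estimand 1 MMRM difference.

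The cost is one SAP paragraph and some programming; no new data are needed. The Estimand 2 imputations cannot be reused, because they are copy-reference and include data after discontinuation. A new MAR model is needed for each of the two SDI scores, with about 43 participants per arm and simulation inside each imputation. The result relies on MAR, as the primary MMRM already does.

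If this is judged too much for an exploratory analysis, the minimum is to state that the result applies to participants with both scores observed at Day 43 and to show that subset's total effect beside the MMRM estimate.
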